**Table 5. Proportion of Children 12-17 yrs. old who completed COVID-19 vaccination by July 31, 2021**

	12-17 Med[IQR]	16-17 years old	14-15 years old	12-13 years old
Overall	30% [25%-42%]	40% [32%-51%]	29% [24%-41%]	24% [19%-34%]
IDeA State Residents	24% [20%-37%]	33% [26%-49%]	23% [19%-35%]	20% [14%-32%]
IDeA State Residents (excluding New England)	23% [19%-36%]*	31% [26%-45%]	22% [18%-29%]	19% [14%-31%]
Non-IDeA State Residents	32% [25%-42%]	41% [32%-51%]	29% [24%-41%]	25% [19%-34%]

\*Difference from non-IDeA state residents (p=0.028)

We based the 10% increase in vaccination rates on the cumulative estimated effects of intervention components within the Vaccine Uptake app. As discussed in the Background, behavioral nudges such as text messages (i.e., push notifications within the app) are associated with a 5% increase in vaccination rates. App-based education and communication has shown variable increases in vaccination rates and intent to vaccinate, up to 8-10%.

**Title:** Improving pediatric COVID-19 vaccine uptake using an mHealth tool: a randomized, controlled trial

**PI:** [name]

Thus, a combined 10% increase in vaccination rates is reasonable to expect from the Vaccine Uptake app since it combines multiple approaches in the same intervention.

**Public Health Impact.** In this study, we are estimating that using the Vaccine Uptake app will result in a 10% increase in the proportion of children who will complete COVID-19 vaccination. When looking at the impact of a 10% increase in pediatric vaccination rates, based on a US population of 53.7 million children 5-17 years of age, such an increase would result in an additional 5 million vaccinated children. Previous research has shown that app-based vaccine uptake interventions are less costly than more traditional methods, such as paper handouts and communication tools. We estimate a cost of \$10,000 dollars for the first year of a customized version of the Vaccine Uptake app per state. Deployment of the Vaccine Uptake app nationally would cost a little as \$500,000 dollars per year, or 10 cents per additional child who completes COVID-19 vaccination.

In determining sample size, each caregiver is considered to be a cluster with an average of 2 unvaccinated children. To demonstrate an improvement in the proportion of unvaccinated children of caregivers who complete the COVID-19 vaccination series due to the mHealth intervention from 30% to 40% would require 758 caregivers (379 per arm), at the two-sided 0.05 significance level with power of 0.90 and an intraclass correlation coefficient of 0.60. The table below shows the sample size needed to have 90% power to detect a 10-percentage point increase in the proportion of children who complete the vaccination series using the Vaccine Uptake app with varying levels of intraclass correlation. To ensure that there are at least 758 caregivers, the primary analysis population, we expect to randomize 892 caregivers to account for up to 15% of randomized participants who do not use the Vaccine Uptake app or General Health app after downloading it during enrollment.

Intraclass Correlation Coefficient	Sample Size
0.40	331 per arm (662 total)
0.50	355 per arm (710 total)
0.60	379 per arm (758 total)
0.70	402 per arm (804 total)
0.80	426 per arm (852 total)

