#### Parent/caregiver inclusion criteria:

- Age of majority, as defined by the state of residency
- Access to a mobile device that can store and run the study app for 24 weeks. Devices that can run the app include mobile phones and tablets running Android or iOS operating systems
- Able to speak and read in English or Spanish
- Be a parent/caregiver with primary medical decision-making and legal authority to consent to vaccination decisions for at least one child who meets the child inclusion criteria

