## 8.3 MEASURES TO MINIMIZE BIAS: RANDOMIZATION

**Randomization:** The study will use a 1:1 parallel design at the caregiver level to assign caregivers to the intervention (Vaccine Uptake app) or the control (General Health app) arm. The study team will stratify randomization by participating clinic and in varying block of participants using a permuted design. Randomization will occur after enrollment and before the baseline assessment.

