### 11.4.2 ANALYSIS OF THE PRIMARY EFFICACY ENDPOINT(S)

**COVID-19 Vaccine Series Completion.** For each vaccine-eligible child, the primary endpoint will be whether or not the child initiates and completes the COVID-19 vaccine series during the 24 weeks of the intervention period. The study team will define vaccine series completion as per the current ACIP guidance for the vaccine product. For children who receive a product that requires more than 2 doses for the primary series, receipt of up to 3 doses will be considered complete. Vaccine doses will only be valid for study purposes if given within the 24 weeks of study participation. Additional doses, when required for primary series completion, will only be valid if they are in accordance with ACIP-recommended interval minus a 4-day grace period, in accordance with recommendations of the ACIP. Also, per ACIP, there will be no maximum interval between valid doses. Incorrect second vaccine product (i.e., mixed series) will be invalid for study purposes. The statistical team will use a mixed model with the binomial distribution and the logit link to compare the two intervention groups with respect to the proportions of children who complete COVID-19 vaccination, using a site random effect and controlling for clustering by caregiver.

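### The sample size table assumes exactly two children per caregiver although the text says an average of two, so each row is too small for its own ICC once family size varies

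*Protocol*

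**What the plan says.** Protocol 11.2, repeated in SAP 3.3, sizes the trial on children nested within caregivers: "each caregiver is considered to be a cluster with an average of 2 unvaccinated children". The target is a rise in completion from 30% to 40%, "at the two-sided 0.05 significance level with power of 0.90" and "an intraclass correlation coefficient of 0.60". The result is 379 caregivers per arm, 758 in total. A table repeats the calculation for ICCs from 0.40 to 0.80. The total is then raised to 892 to allow for up to 15% who do not use the app.

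Three other provisions bear on cluster size:

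- Protocol 6.1.1 admits a caregiver with decision-making authority "for at least one child who meets the child inclusion criteria". There is no maximum.
- Protocol 11.4.2 defines the outcome per child: "For each vaccine-eligible child, the primary endpoint will be whether or not the child initiates and completes" the series.
- Protocol 8.3 randomizes caregivers, not children: "The study will use a 1:1 parallel design at the caregiver level".

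Neither document gives a standard deviation, CV or distribution for the number of eligible children per caregiver, or any allowance for unequal clusters.

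**The concern.** With a minimum of one child and a mean of two, cluster size is constant only if every caregiver has exactly two eligible children. Otherwise some have one and others three or more. At a given mean, unequal clusters carry less information than equal ones, so a design effect for exactly two understates the number of caregivers needed.

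The table varies the ICC but silently fixes cluster size, which is the other component of the design effect. What is at stake is the stated power. A reader who has to interpret a null result would take 90% at 758 caregivers as given, when it holds only in the equal-size case.

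**Working it through.** **Inputs from Protocol 11.2:** two-sided alpha 0.05 (z = 1.960), power 0.90 (z = 1.2816), 30% versus 40%, mean 2 children, ICC 0.60 (table 0.40 to 0.80). **Assumed, because the documents are silent:** the CV or distribution of children per caregiver.

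**1. Reproduce the plan.** Children per arm if independent, unpooled variance:

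(1.960 + 1.2816)² × (0.30×0.70 + 0.40×0.60) / 0.10² = 472.8

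Caregivers per arm = 472.8 × [1 + (2 − 1) × ICC] / 2:

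| ICC | Computed | Plan |
|---|---|---|
| 0.40 | 330.98 | 331 |
| 0.50 | 354.63 | 355 |
| 0.60 | 378.27 | 379 |
| 0.70 | 401.91 | 402 |
| 0.80 | 425.55 | 426 |

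All five rows match. Power at 379 per arm is 90.05%. Also 758 / 0.85 = 891.8, which gives 892.

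**2. Unequal sizes, children weighted equally.** Design effect = 1 + [(1 + CV²) × 2 − 1] × ICC. Caregivers per arm = 472.8 × design effect / 2. Power = Φ(0.10 / √(0.45 / n_eff) − 1.960), where n_eff = caregivers per arm × 2 / design effect. At ICC 0.60:

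| Assumed CV | Design effect | Caregivers for 90% | Power at 758 | Power at 892 |
|---|---|---|---|---|
| 0 | 1.600 | 758 | 90.05% | 94.1% |
| 0.3 | 1.708 | 808 | 88.1% | 92.6% |
| 0.4 | 1.792 | 848 | 86.6% | 91.4% |
| 0.5 | 1.900 | 900 | 84.6% | 89.8% |
| 0.6 | 2.032 | 962 | 82.1% | 87.8% |

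The 892 column assumes that all randomized caregivers contribute outcomes and that the full 10-point effect applies. On that basis power stays at or above 90% up to a CV of about 0.49.

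**3. Unequal sizes, efficient cluster weighting.** A caregiver with m children contributes m / [1 + (m − 1) × ICC] effective children. At ICC 0.60 this is 1, 1.25, 1.364 and 1.429 for m = 1, 2, 3 and 4. Against 1.25 for exactly two:

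- Sizes 1/2/3 at 25/50/25% (mean 2, CV 0.35): 0.25×1 + 0.50×1.25 + 0.25×1.364 = 1.216. Needs 472.8 / 1.216 = 388.9, so 389 per arm (778). Power is 89.3% at 758 and 93.5% at 892.
- Sizes 1/2/3/4 at 40/30/20/10% (mean 2, CV 0.5): 0.40×1 + 0.30×1.25 + 0.20×1.364 + 0.10×1.429 = 1.191. Needs 397.1, so 398 per arm (796). Power is 88.6% at 758 and 93.0% at 892.

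**4. Direction.** The design effect in step 2 rises with CV². The contribution in step 3 is concave in m, so at a fixed mean of two any spread lowers its average. Each table row is therefore too small for its own ICC under either weighting.

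**5. Simulation check.** Beta-binomial outcomes at 379 per arm, sizes 1/2/3 at 25/50/25%, gave 87.4% with equal child weighting (formula 87.3%) and 88.3% with efficient weighting (formula 89.3%). Agreement is to about one point.

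**The case against.** The strongest case on the other side has four parts.

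- **Nothing is miscalculated.** The table and the 892 reproduce exactly, and 90% at 758 is right for two children each. This stands: the fault is an unstated simplification, and the text describes the cluster size as an average.
- **The larger losses depend on how the model weights children.** Protocol 11.4.2 specifies a logit mixed model and SAP 6.2 a mixed-effect Poisson model with robust variance. Both say they control for caregiver clustering, and neither says how. A caregiver random effect would weight closer to efficiently, where the loss at 758 is about 1 to 1.5 points for the mixes tried. This stands, and it is why both weightings are shown.
- **The plan randomizes 892 and analyses by ITT** (Protocol 11.3, SAP 5.3). At the full effect that surplus covers a moderate spread. This largely stands, but Protocol 11.2 sets the surplus aside for non-use. Under ITT non-users remain in the analysis and can dilute the effect. As an illustration, if 15% of the intervention arm gained nothing, the difference would be 38.5% − 30% = 8.5 points. Power at 892 would be 85.1% with exactly two children, and 78.7% at CV 0.5 with equal child weighting (83.4% for the 40/30/20/10% mix with efficient weighting). The surplus cannot be counted in full against both problems.
- **The table already runs to ICC 0.80**, where 852 caregivers cover the CV 0.4 case at ICC 0.60 (848). This is true numerically, but a reader cannot tell that the ICC range is standing in for family-size spread.

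A reader might also infer that 758 is short at every ICC in the table. It is not: with equal child weighting it still gives 90.05% at ICC 0.40 with CV 0.5, and 90.2% at ICC 0.50 with CV 0.3. It is each row's own figure that is too small for that row's ICC.

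**Conclusion.** The point holds for the stated calculation. At ICC 0.60, 758 caregivers do not give 90% power once family size varies around a mean of two. The shortfall at 758 is roughly 1 to 8 points: about 2 to 8 with equal child weighting for CVs of 0.3 to 0.6, and about 1 to 1.5 with efficient weighting for the two mixes shown. The direction follows from the documents' own inputs. The size rests on assumed spreads, and on a weighting that neither document settles.

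It would be tempting to conclude that the trial as planned is underpowered or must enrol more. The documents do not support that. With all 892 analysed at the full 10-point effect, power is 92.6%, 91.4%, 89.8% and 87.8% for CVs of 0.3, 0.4, 0.5 and 0.6 with equal child weighting, and about 93% for both mixes with efficient weighting. Dilution by non-users would lower these figures, but that is a separate question.

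**What to change.** In Protocol 11.2 and SAP 3.3:

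1. State the assumed distribution or CV of eligible children per caregiver, and its source.
2. Replace the constant-size design effect with the unequal-cluster form, 1 + [(1 + CV²) × mean − 1] × ICC, and give the efficient-weighting counterpart.
3. Qualify the 90% at 758 as holding only for exactly two eligible children per caregiver.
4. Tabulate power at both 758 and 892 for CVs of 0.3 to 0.6 under both weightings, and state whether the 892 figures allow for dilution by non-users.

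The cost is two or three sentences and one table. No extra enrolment is needed, and no endpoint, analysis population or test changes. The price is a stated power at 758 that is about 1 to 8 points lower.

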### 11.3 POPULATIONS FOR ANALYSES

This study will have three analysis populations:

1. ITT population – This population will include all participants randomized into the study.

**Title:** Improving pediatric COVID-19 vaccine uptake using an mHealth tool: a randomized, controlled trial

**PI:** [name]

2. Modified ITT (mITT) population – This population will include all participants who are randomized into the study, were eligible for the study, and completed at least one session in the app involving the use of at least one pathway.
3. Per-protocol (PP) population - This population will include all participants in the mITT population who were maintained in the study for the full 27 weeks.

The primary population for analysis will be the ITT population. Study statisticians will perform additional analyses on the PP and mITT populations.

## 11.4 STATISTICAL ANALYSES

### 11.4.1 GENERAL APPROACH

Following finalization of the protocol, but prior to data lock, the DCOC statistical team will issue a Statistical Analysis Plan (SAP) as a separate document, which will provide detailed analytical plans for the set of analyses outlined below. The statistical team will conduct all statistical analyses following the statistical principles for clinical trials as specified in ICH Statistical Principles for Clinical Trials (ICH Topic E9). The study team will describe and justify any deviations from the planned analyses in the final integrated clinical study report. The study team will present all study data and summary tables for the overall study and by study sites.

The statistical team will summarize descriptive statistics for continuous data by using mean and standard deviation or median and interquartile range, as appropriate. The team will also summarize categorical data by using frequency and percent, and they will investigate any outliers detected during data review and will define in the SAP methods for handling outliers or data transformation.

### 11.4.2 ANALYSIS OF THE PRIMARY EFFICACY ENDPOINT(S)

**COVID-19 Vaccine Series Completion.** For each vaccine-eligible child, the primary endpoint will be whether or not the child initiates and completes the COVID-19 vaccine series during the 24 weeks of the intervention period. The study team will define vaccine series completion as per the current ACIP guidance for the vaccine product. For children who receive a product that requires more than 2 doses for the primary series, receipt of up to 3 doses will be considered complete. Vaccine doses will only be valid for study purposes if given within the 24 weeks of study participation. Additional doses, when required for primary series completion, will only be valid if they are in accordance with ACIP-recommended interval minus a 4-day grace period, in accordance with recommendations of the ACIP. Also, per ACIP, there will be no maximum interval between valid doses. Incorrect second vaccine product (i.e., mixed series) will be invalid for study purposes. The statistical team will use a mixed model with the binomial distribution and the logit link to compare the two intervention groups with respect to the proportions of children who complete COVID-19 vaccination, using a site random effect and controlling for clustering by caregiver.

#### **11.4.3 ANALYSIS OF THE SECONDARY ENDPOINT(S)**

**Vaccine Series Initiation.** For each vaccine-eligible child, this secondary endpoint will be defined as whether or not the child initiates the COVID-19 vaccine series during the 16 weeks of study participation. Vaccine series initiation will be receipt of at least 1 valid dose of any COVID-19 vaccine product. Vaccine doses for series initiation will only be valid for study purposes if given within the 16 weeks of study participation. The statistical team will use a mixed model with the binomial distribution and the logit link to compare the two intervention groups with respect to the proportions of children who initiate COVID-19 vaccination, using site as a random effect and controlling for clustering by caregiver.

**Parental attitude toward pediatric COVID-19 vaccination.** The study team will evaluate parental attitude toward pediatric COVID-19 vaccination by using the vaccine hesitancy questionnaire that includes ten statements with ordinal responses using a 5-point Likert scale. At baseline and week 16, the study statisticians will generate summary statistics for each of the 10 questions for the two intervention groups. Similarly, the change in responses from baseline to end of study will be determined for each intervention group. The study statisticians will use the general linear mixed model to evaluate the intervention effect on responses to each measure at baseline and end of study, and they will use this model to evaluate the change in each measure by using site as a random effect. Within each intervention arm and for each statement, the study statisticians will use the Wilcoxon signed rank test to determine if the change in response from baseline to end of study is significantly different from zero.

---

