#### **Changes from Version 09 to Version 10**

Affected Section(s)	Summary of Revisions Made	Rationale
1.1	Updated participant duration	Reflect extended duration of vaccine status follow-up
1.2	Corrected dates without push notifications. Updated vaccine verification status	Correction and reflect extended vaccine verification period
1.3.1	Updated all activities after participant recruitment. Added 3 months to study timeline.	Reflect extended periods because of extended participant activities to include week 24 survey and extended vaccine verification period.
1.3.2	Extended vaccine status follow-up period	Reflect change that period lasts until week 29
5.3	Extended vaccine status follow-up period	Reflect change that period lasts until week 29
10.1	Changed secondary endpoint #1 from 16 weeks to 24 weeks	Correction

---

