**Description of Study Intervention:**

- **Vaccine Uptake App:** 24-week (8 weeks with weekly push notifications; 2 monthly push notifications for 2 months [1 notification per month]; 8 weeks without) exposure to a mobile phone application (app) designed to improve parental knowledge, attitudes, and self-efficacy regarding pediatric COVID-19 vaccination. The app will address logistical and motivational barriers to pediatric COVID-19 vaccination. Participants will also receive eight weekly nudges (cues to action) regarding vaccinating their child that will be sent to participants via push notifications to their mobile devices. Through branching logic, users will access content tailored to their COVID-19 vaccine knowledge and confidence gaps, locality, degree of rurality-urbanicity, primary language (English/Spanish), race/ethnicity, and child's age.
- **General Health App:** 24-week (8 weeks with weekly push notifications; 2 monthly push notifications for 2 months [1 notification per month]; 8 weeks without) exposure to a mobile phone app designed to provide information on general pediatric health and infection prevention and mitigation strategies based on recommendations from the American Academy of Pediatrics (AAP) and the Centers for Disease Control and Prevention (CDC). Nudges regarding these topics will be sent to participants via push notifications to their mobile devices.

[figure not shown]
**Study Duration:** 24 months (6 months study start-up; up to 8 months rolling enrollment; 7 months final participants' completion; 3 months analysis)

**Title:** Improving pediatric COVID-19 vaccine uptake using an mHealth tool: a randomized, controlled trial

**PI:** [name]

**Participant** 28 weeks (8 weeks with weekly push notifications; 2 monthly push notifications for 2 months  
**Duration:** [1 notification per month]; 8 weeks without notifications; 4 weeks participant vaccine status follow-up)

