#### 4. OBJECTIVES AND ENDPOINTS

OBJECTIVES	ENDPOINTS	JUSTIFICATION FOR ENDPOINTS
Primary		
Objective 1: Determine the effect of a parent-facing, vaccination decision-making mHealth tool on children's COVID-19 vaccine series completion	Proportion of children who complete COVID-19 vaccination, as verified in state, clinic, or participant-held records	The intended goal of the intervention is to increase the number of children receiving a complete COVID-19 vaccine series since series completion provides children with maximal protection afforded by vaccination. Self-report of vaccination will not be used, only verified vaccination records, to avoid introduction of recall and social desirability biases in the assessment of the endpoint. The study team will define vaccine series completion as per the current Advisory Committee on Immunization Practices (ACIP) guidance for the vaccine product. For children who receive a product that requires more than 2 doses for the primary series, receipt of up to 3 doses will be considered complete.
Secondary		
Objective 1: Determine the effect of a parent-facing, vaccination decision-making mHealth tool on children's	Proportion of children who receive ≥1 dose of the COVID-19 vaccination series, as	Some COVID-19 vaccines require completion of a multiple-dose series to achieve intended immunity. A necessary precursor to our primary endpoint of vaccine series completion is vaccine

**Title:** Improving pediatric COVID-19 vaccine uptake using an mHealth tool: a randomized, controlled trial

**PI:** [name]

OBJECTIVES	ENDPOINTS	JUSTIFICATION FOR ENDPOINTS
COVID-19 vaccine series initiation	verified in state, clinic, or participant-held records	series initiation (i.e., receipt of first dose). As more individuals initiate vaccine series than complete it, vaccine series initiation may be a more sensitive indicator of the intervention's effect.
Objective 2: Determine the effect of a parent-facing, vaccination decision-making mHealth tool on parental attitude toward pediatric COVID-19 vaccination	Change in enrolled parent/caregiver domain scores from baseline to week 16 on the modified SAGE Vaccine Hesitancy Scale adapted for the COVID-19 Vaccine	Vaccine hesitancy contributes to vaccination decisions. Measuring any changes in vaccine hesitancy in association with use of the Vaccine Uptake app will provide further insight into the impact of the app on parent/caregiver decision-making.

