## 10. STUDY ASSESSMENTS AND PROCEDURES

### 10.1 EFFICACY ASSESSMENTS

The primary endpoint is child initiation and completion of COVID-19 vaccination by the end of week 24 post caregiver randomization. Verification of vaccine receipt will occur by any of the following methods:

1. Photograph of the child's vaccine card, furnished by the caregiver
2. Medical records documentation of child vaccine receipt
3. Recorded vaccine receipt in the appropriate state vaccine registry

**Title:** Improving pediatric COVID-19 vaccine uptake using an mHealth tool: a randomized, controlled trial

**PI:** [name]

**Secondary endpoint #1** is child receipt of  $\geq 1$  dose of the COVID-19 vaccination series by the end of week 24 post caregiver randomization. Verification of vaccine receipt will be the same as for the primary endpoint.

**Secondary endpoint #2** is enrolled caregiver domain scores on the modified SAGE Vaccine Hesitancy Scale adapted for the COVID-19 Vaccine from baseline and the end of week 16 post caregiver randomization. Caregiver participants will complete this survey electronically.

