1. PURPOSE OF THE STATISTICAL ANALYSIS PLAN

The statistical analysis plan (SAP) is a document intended to provide a detailed and comprehensive layout of the planned analytical methodology to be used for the multi-center randomized study of a vaccine communication mHealth app on parental decisions to vaccinate their children against coronavirus disease 2019 (COVID-19) of UAMS Protocol 273761, Improving Pediatric COVID-19 Vaccine Uptake Using an mHealth Tool: A Randomized, Controlled Trial. This SAP applies to the protocol Version 09 dated on December 16, 2022. The purpose of this plan is to provide general, and in some instances, specific guidelines from which the analysis will proceed.

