6.3 ANALYSIS OF THE SECONDARY EFFICACY ENDPOINT(S)

6.3.1 Vaccine Series Initiation

For the secondary efficacy measure, we will test the following null hypothesis:

H₀: Vaccination series initiation rate among children of caregivers assigned to the Vaccine Uptake app will not differ from the vaccine series initiation rate among children of caregivers assigned to the General Health app

vs

H₁: Unvaccinated children of caregivers assigned to the Vaccine Uptake app will be more likely to achieve COVID-19 vaccine series initiation than those children whose caregivers are assigned to the General Health app

For each vaccine-eligible child, this secondary endpoint will be defined as whether or not the child initiates the COVID-19 vaccine series during the 16 weeks of study participation. Vaccine series initiation will be receipt of at least 1 valid dose of any COVID-19 vaccine product. Vaccine doses for series initiation will only be valid for study purposes if given within the 16 weeks of study participation.

Univariate Analysis

The secondary vaccine series initiation endpoint will be collected as a dichotomous variable (yes/no). We will report the probability of COVID-19 vaccine series initiation for each intervention group (Vaccine Uptake app vs General Health app). Initially, an unadjusted non-modeling approach using SAS PROC FREQ will be used estimate the relative risk (RR) for COVID-19 vaccine series initiation (with Wald 95% CI), with the General Health app intervention group as the reference group. The analysis will be performed for all three populations (ITT, mITT, and PP).

Secondary and Multivariable Analysis

A mixed-effect Poisson regression with robust error variance will be used to report adjusted relative risk (RR) with 95% CI accounting for site random effect and controlling for clustering by caregiver. The multivariable model will allow adjustment for covariates. The analysis will be performed for all three populations (ITT, mITT, and PP).

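### Series initiation is counted to week 24 in protocol 10.1 but only to week 16 in protocol 11.4.3 and SAP 6.3.1

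*Protocol*

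**What the plan says.** Protocol 10.1 defines secondary endpoint 1 as receipt of at least one "dose of the COVID-19 vaccination series by the end of week 24 post caregiver randomization".

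Protocol 11.4.3 uses 16 weeks twice, once in defining the endpoint and once in its dose-validity rule: "Vaccine doses for series initiation will only be valid for study purposes if given within the 16 weeks of study participation". SAP 6.3.1 repeats both statements and asks whether the "child initiates the COVID-19 vaccine series during the 16 weeks of study participation".

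The endpoint lists in protocol sections 1.1 and 4 and in SAP section 4 give no time limit for initiation, so they do not settle the matter.

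For the primary endpoint, completion, protocol 11.4.2 and SAP 6.2 agree on 24 weeks: "Vaccine doses will only be valid for study purposes if given within the 24 weeks of study participation".

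Two statements bear on intent. The version 10 log entry for section 10.1 reads "Changed secondary endpoint #1 from 16 weeks to 24 weeks", gives the rationale as a correction, and lists no change to 11.4.3. SAP section 1 states "This SAP applies to the protocol Version 09 dated on December 16, 2022".

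**The concern.** The endpoint cannot be computed without choosing between two rules. An analyst who follows the SAP will use a window that protocol 10.1 no longer carries, and the reported initiation rates will depend on which section was followed. SAP 3.2.2 plans no masking, so a choice left until results are visible would be open to the charge of post hoc selection.

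The 16-week rule also breaks the ordering of the two vaccination endpoints. Protocol section 4 justifies initiation in these terms: "A necessary precursor to our primary endpoint of vaccine series completion is vaccine" series initiation. With completion counted to week 24 and initiation only to week 16, those who complete need not be a subset of those who initiate.

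**Working it through.** **The windows side by side**

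| Source | Endpoint | Window |
|---|---|---|
| Protocol 10.1 | Initiation | 24 weeks |
| Protocol 11.4.3 (twice) | Initiation | 16 weeks |
| SAP 6.3.1 (twice) | Initiation | 16 weeks |
| Protocol 10.1, 11.4.2; SAP 6.2 | Completion | 24 weeks |

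All of these are current text. The change log serves only as evidence of intent.

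**The period in dispute.** 24 × 7 − 16 × 7 = 168 − 112 = 56 days, that is days 113-168, or 8 of the 24 weeks.

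**Who is scored completion = 1 and initiation = 0.** The first dose falls on day d with 113 ≤ d ≤ 168, and the last dose must fall by day 168. Let S be the nominal minimum span of the series in weeks and k the number of doses after the first, each with the 4-day grace of protocol 11.4.2. The last dose can then fall no earlier than d + 7S − 4k, so the number of qualifying start days is max(0, 56 − 7S + 4k). The documents do not give the intervals, so the values of S are assumptions.

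| Series | Span S (weeks) | Calculation | Start days out of 56 |
|---|---|---|---|
| Two doses (k = 1) | 3 | 56 − 21 + 4 | 39 |
| | 4 | 56 − 28 + 4 | 32 |
| | 6 | 56 − 42 + 4 | 18 |
| | 8 | 56 − 56 + 4 | 4 |
| | 9 | 56 − 63 + 4 < 0 | 0 |
| Three doses (k = 2) | 8 | 56 − 56 + 8 | 8 |
| | 9 | 56 − 63 + 8 | 1 |
| | 10 | 56 − 70 + 8 < 0 | 0 |

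If a single-dose series counted as complete (S = 0, k = 0), all 56 days would qualify. These are counts of possible start dates, not of children.

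**The plan's own sample size, reproduced.** Inputs from protocol 11.2: 30% vs 40%, two-sided 0.05, power 0.90, 2 children per caregiver, ICC 0.60.
- Children per arm before clustering: (1.960 + 1.282)² × (0.3 × 0.7 + 0.4 × 0.6) / 0.10² = 472.8.
- Design effect: 1 + (2 − 1) × 0.60 = 1.6.
- Caregivers per arm: 472.8 × 1.6 / 2 = 378.3, rounded up to 379, or 758 in total.
- Inflation: 758 / 0.85 = 891.8, rounded up to 892.

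This rests on completion only. The plan states no power for initiation.

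**Illustrative power for initiation.** As an assumption, take 30% vs 40% as the week-24 initiation rates. With 446 caregivers per arm (892 / 2, the ITT population), effective n = 446 × 2 / 1.6 = 557.5 per arm. Power = Φ(difference / SE − 1.960), with SE = √[(p₁q₁ + p₂q₂) / 557.5].

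| First doses lost by stopping at week 16 | Rates | Power |
|---|---|---|
| None | 30% vs 40% | 94.1% |
| 10% of doses in each arm | 27% vs 36% | 90.1% |
| 20% in each arm | 24% vs 32% | 84.8% |
| One third in each arm | 20% vs 26.7% | 75.2% |
| 3 points in each arm | 27% vs 37% | 94.9% |
| 6 points in each arm | 24% vs 34% | 95.9% |
| 10 points in each arm | 20% vs 30% | 97.3% |

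At 379 caregivers per arm, no loss and the three proportional losses give about 90%, 85%, 78% and 68%. Proportional loss lowers power and equal absolute loss raises it, so the direction cannot be determined.

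**The case against.** The strongest counter-argument is that 16 weeks may be deliberate. The version 06 log lists 10.1, 11.4.2 and 11.4.3 as updated together for the three-dose redesign, so 11.4.3 was revisited then. Sixteen weeks is also the period of scheduled notifications (8 weekly, then 2 monthly); the synopsis follows it with "8 weeks without notifications; 4 weeks participant vaccine status follow-up". Counting first doses over that period and leaving the later weeks to finish the series would be coherent, and endpoints with different windows can disagree for a child without either being wrong. The SAP text shows no issue date, so whether it was written before or after version 10 cannot be established.

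What stands is that a missed edit is an inference. It remains the better reading. The later log entry calls 24 weeks in 10.1 a correction. No current section defines participation as 16 weeks. The primary endpoint already requires a child both to start and to finish within 24 weeks. If 16 weeks were wanted, 10.1 would be the section in error, and the passages would still have to be reconciled.

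Some limits on the numbers also stand. The 30% and 40% are completion rates, and protocol section 4 expects more children to initiate than to complete. The one-third loss corresponds to even timing of first doses over 24 weeks and is shown only as an upper case. Weeks 17-24 lack scheduled notifications, but protocol 7.2 and 8.1.3 provide for ad hoc ones. None of this changes the conflict between the sections.

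**Conclusion.** The concern holds. Secondary endpoint 1 has a 24-week window in one current section and a 16-week window in two others, and the documents do not say which the analysis will use. The weight of evidence favours 24 weeks.

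The 16-week rule leaves out first doses on 56 of 168 days. How many children that involves is not in the documents. The mismatch with completion arises for short series and, on the assumed intervals, disappears from a 9-week span with two doses and a 10-week span with three. The power figures are illustrations on assumed rates and give no direction. The damage is confined to secondary endpoint 1, but it has to be settled before data lock because the endpoint has no single definition.

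**What to change.** Before data lock:
- Change both 16-week statements on initiation in protocol 11.4.3, and both in SAP 6.3.1, to 24 weeks after caregiver randomization, matching protocol 10.1 and the completion window.
- Update SAP section 1 to refer to protocol version 10 and check the rest of the SAP against that version.
- Leave the week-16 hesitancy assessment (secondary endpoint 2) as it is.
- Initiation by week 16 may be kept as a descriptive supplement, labelled as such.

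The cost is four wording changes, a reissued SAP, and the IRB review that the protocol's Statement of Compliance requires for any amendment. No new data are needed, since vaccine status to week 24 is already collected and verified for the primary endpoint.
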